#### q Biopsy is mandatory unless medically contraindicated.

- r PRO questionnaires will be implemented in Part B once available at the site. Baseline PRO questionnaires must be administered after informed consent and before the first dose of study drug. Subsequent PRO questionnaires may be completed at home or at the site. If PRO questionnaires are completed at the site on dosing dates, then they must be completed prior to treatment administration.
-  Each dose of sabestomig will be infused over approximately 60 minutes (-5 min to +15 min). Participants should be closely monitored during and after infusions, as described in Section 6.2.1.2. Following completion of the first treatment cycle, participants may receive additional treatment with sabestomig if dosing criteria defined in Section 6.1.2 are met. For participants with a known previous COVID-19 infection in the last 3 months, a negative PCR test must be documented within 72 hours prior to the first dose of sabestomig. In the event of a COVID-19 infection while on active treatment with sabestomig, the investigator should use their judgement to delay treatment depending on the clinical situation of the participant (see also Section 6.7).
- t At least 10 days post infusion, but prior to the next infusion. Disease response should be assessed by PET-CT as per Modified Lugano criteria (2014) until participant achieves CR. Once CR is achieved, contrast CT may replace PET-CT to monitor disease response until PD is suspected. If PD suspected, PD must be confirmed by PET CT scan. Disease response assessments will be assessed by both the Investigator according to Modified Lugano (Cheson et al, 2014) and RECIL (Younes et al, 2017) criteria and Blinded Independent Central Review according to Modified Lugano.

Abbreviations: ADA: anti-drug antibody; AE: adverse event; anti-HBc: hepatitis B core antibody; anti-HBs: antibody to hepatitis B surface antigen; C: cycle; COVID-19: coronavirus disease; CR: complete response; CT: computed tomography; D: day(s); ECG: electrocardiogram; EOI: end of infusion; COVID-19: coronavirus disease; CR: complete response; CT: computed tomography; D: day(s); ECG: electrocardiogram; EOI: end of infusion; COVID-19: coronavirus disease; CR: complete response; CT: computed tomography; D: day(s); ECG: electrocardiogram; EOI: end of infusion; COVID-19: coronavirus disease; CR: complete response; CT: computed tomography; D: day(s); ECG: electrocardiogram; EOI: end of infusion; COVID-19: coronavirus disease; CR: complete response; CT: computed tomography; D: day(s); ECG: electrocardiogram; EOI: end of infusion; COVID-19: coronavirus disease; CR: complete response; CT: computed tomography; D: day(s); ECG: electrocardiogram; EOI: end of infusion; COVID-19: coronavirus disease; CR: complete response; CT: computed tomography; D: day(s); ECG: electrocardiogram; EOI: end of infusion; COVID-19: coronavirus disease; CR: complete response; CT: computed tomography; D: day(s); ECG: electrocardiogram; EOI: end of infusion; COVID-19: coronavirus disease; CR: complete response; CT: complet

; EoS: end of study; EoT: end of treatment; CC

; HbsAg: hepatitis B surface antigen; h: hour; HL: Hodgkin lymphoma; min: minute; PCR: polymerase chain reaction; PD: progressive disease;
 ; PET-CT: positron emission tomography-CT; PF: pediatric short form; PGI-TT: Patient Global Impression of Treatment Tolerability;
 PGIC: Patient Global Impression of Change;
 CCI
 <li

PRO-CTCAE: Patient-Reported Outcomes version of the Common Terminology Criteria for Adverse Events; Q1W: every week; Q3W: every 3 weeks; Q6M: every 6 months; Q6W: every 6 weeks; RECIL: Response Evaluation Criteria in Lymphoma; RT: radiation therapy; SAE: serious adverse event; SF: short form; SOI: start of infusion; TIM-3: T cell immunoglobulin and mucin domain-containing protein-3; V: visit.

	At Disease Progression a	EoT b	Post-treatment Safety Follow-up c		Survival Follow-up c	
Procedure/Visit (Window)		+ 14 D	Day 30 Post Last Dose (± 7 D)	Day 90 Post Last Dose (± 7 D)	Q6M Post Last Disease Assessment (± 14 D)	
Abbreviated (symptom-directed) physical examination including weight (Section 8.2.2)		Х	Х	Х		
12-lead ECG (triplicate) (Section 8.2.4)		X				
Left ventricular ejection fraction by echocardiogram/ multiple-gated acquisition scan (Section 8.2.5) d		Х	If clinically indicated.			
Vital signs including pulse oximetry (Section 8.2.3)		Х	Х	Х		
Eastern Cooperative Oncology Group performance status (Section 8.2.6)		Х	Х	Х		
Assessment of B-Symptoms (Section 8.1.1)		X	Х	Х		
Assessment of AEs/SAEs (Section 8.3)		←	XX	→		
Concomitant medications (Section 6.5)		←→				
Subsequent anticancer therapy	Х	X	Х	Х	X	
Survival status (by telephone, email, or clinic visit)	Х	X	X	Х	X	
Disease status post HSCT if applicable (by telephone, email, or clinic visit) e					Х	
Blood and Urine Tests		·			·	
Clinical Chemistry (Section 8.2.7)		Х	Х	Х		
Hematology (Section 8.2.7)		Х	Х	Х		
Glycated hemoglobin (Section 8.2.7)		Х		Х		
Thyroid function (thyroid-stimulating hormone, free thyroxine, and free triiodothyronine as indicated f ; Section 8.2.7)		Х	x	Х		
Anti-thyroid antibodies (anti-thyroid peroxidase antibodies, thyroglobulin antibodies, thyrotropin receptor antibodies; Section 8.2.7)		Х	X	Х		
Hepatitis B and C virology (Section 8.2.7) g			Х			

#### Table 4Schedule of Activities for Disease Progression, End of Treatment, and Follow-up Period (Parts A and B)

CONFIDENTIAL AND PROPRIETARY

Table 4	Schedule of Activities for	Disease Progression ,	End of Treatment .	and Follow-u	p Period (	Parts A and B	)
		······································					

	At Disease Progression a	EoT b Post-treatment		Safety Follow-up c	Survival Follow-up c	
Procedure/Visit (Window)		+ 14 D	Day 30 Post Last Dose (± 7 D)	Day 90 Post Last Dose (± 7 D)	Q6M Post Last Disease Assessment (± 14 D)	
Pregnancy test (urine or serum; women of child-bearing potential only; Section 8.2.7)		Х	X	Х		
Urinalysis (Section 8.2.7)		Х	X			
Blood Tests for PK and Immunogenicity						
Part A Dose Escalation and Part B for patients from mainland China: Serum for sabestomig PK (Section 8.5)		Х	X			
Part A Dose Escalation and Part B for patients from mainland China: Serum for sabestomig ADA (Section 8.5)		Х	Х	Х		
Blood Tests for Biomarker Evaluations h						
Whole blood for CCI (Section 8.6.1) i	х	Х	X			
Whole blood for CCI (flow) (Section 8.6.1) i	Х	Х				
Serum for CCI (Section 8.6.1) i	X	Х	Х			
Serum for CCI analysis (Section 8.6.1) i	X	Х	Х	Х		
Whole blood for CCI and circulating biomarkers (Section 8.6.1) i	Х	Х	X	Х		
Whole blood for CCI (Section 8.6.1) i	Х	Х	Х			
PRO Collection (Part B only)						
Tolerability [Adults: PRO-CTCAE + PGI-TT Adolescents: Peds-PRO-CTCAE]		Xj				
Physical function [Adults CC] Adolescents: CC		Xj				
Table 4	Schedule of Activities for I	Disease Progression.	End of Treatment.	and Follow-up Period	d (Parts A and B)	
---------	------------------------------	-----------------------------	--------------------------	----------------------	-------------------	

		EoT b		Post-treatment Safety Follow-up c	
Procedure/Visit (Window)	Progression a + 14 D	Day 30 Post Last Dose (± 7 D)	Day 90 Post Last Dose (± 7 D)	Q6M Post Last Disease Assessment (± 14 D)	
Disease symptoms and health status [Adults: CCI Adolescents: CCI		X j			
Biopsies j, h					
Optional tumor tissue biopsy (Section 8.6.2.1) k	Х	$X^k$			
Non-tumor tissue biopsy (Section 8.6.2.2)	At toxicity, if clinically indicated				
Disease Assessments					
Imaging disease assessment (Section 8.1, Table 16) 	At least 10 days after sabestomig administration in Cycle CC and CC then thereafter at Year 1 then Q6M to be continued beyond the Day 90 post last dose visit if participant still in response, until PD, start of new treatment for cHL or EoS (whichever occurs first)				
a This visit is only required for participants who discontinued for disease progression.					

b The EoT visit can be combined with the Day 30 post-last dose follow-up visit if timelines/windows overlap. At this combined visit, required tests and assessments between both the EoT and Day 30 post last dose visit must be performed, ensuring there are no duplicates. If the participant is planned to continue on sabestomig treatment at the time of the final study DCO and as the study transitions to PTAP, the EoT visit will not be performed. The participant will complete the last dosing visit per SoA Table 2 before the final DCO.

c All participants in Safety or Survival follow-up at the time of final study DCO will be contacted by the study site prior to the final study DCO to confirm their survival status and to inform participants that this was the last study-related contact, and no further survival data will be collected in respect to the study. Sites are requested to document this last contact in the source records.

d If clinically indicated, and at the Investigator's discretion, a consultation with a cardiologist is recommended for follow-up.

e To be collected only for participant who received any dose of the study drug and underwent HSCT while in response (CR or PR) without any other treatment between last dose of sabestomig and start of pre-conditioning for HSCT.

f Free thyroxine and triiodothyronine only to be measured if thyroid-stimulating hormone is abnormal or if suspicion of an adverse event related to the endocrine system.

g Hepatitis B virology testing during treatment and follow-up is required for participants with positive HbsAg or isolated positive anti-HBc (negative HbsAg and negative anti HBs) at screening and for any participant where clinically indicated. Participants with positive HbsAg must remain on antiviral therapy, per institutional practice, to ensure adequate viral suppression during the study intervention and follow-up periods. Controlled hepatitis B viral load is defined as serum hepatitis B virus DNA < 100 IU/mL by PCR.

Hepatitis C virology testing during treatment and follow-up is only required for participants with positive hepatitis C antibody at screening and for any participant where clinically indicated. Controlled hepatitis C viral load is defined as undetectable hepatitis C virus RNA by PCR either spontaneously or in response to a successful prior course of anti-hepatitis C therapy.

h These samples will not be collected in mainland China.

i All ECGs will be obtained in triplicate (all within a 5-minute time period). Whenever ECGs and blood draws (eg, PK/ADA) are scheduled for the same nominal time, the blood draws should occur last. The timing of the ECG should be such that it allows the blood draw to occur at the proper nominal time.

j Refer to Vendor's Study Information Guide and training for window of completion.

- k Optional biopsy at EoT is to be performed only for participants who discontinue treatment due to disease progression and if participant has consented for the optional procedure. If the participant begins a new treatment shortly after discontinuation and within the 14-day allowable EoT biopsy window, a biopsy should not be collected.
-  During the intervention period, the imaging to be performed at least 10 days post infusion. Disease response should be assessed by PET-CT as per Modified Lugano criteria (2014) until participant achieves CR. Once CR is achieved, contrast CT may replace PET-CT to monitor disease response until PD is suspected. If PD is suspected, PD must be confirmed by PET. Disease response assessments will be assessed by both the Investigator according to Modified Lugano (Cheson et al, 2014) and RECIL (Younes et al, 2017) criteria and Blinded Independent Central Review according to Modified Lugano. Schedule is detailed in Table 16.

Abbreviations: ADA: anti-drug antibody; AE: adverse event; anti-HBe: hepatitis B core antibody; anti-HBs: antibody to hepatitis B surface antigen; cHL: classical Hodgkin disease; CR: complete response; CT: computed tomography; D day(s); DCO: data cut-off; ECG: electrocardiogram; CCI

; EoS: end of study; EoT: end of treatment; CC	; HbsAg: hepatitis B surface
antigen; HSCT: hematopoietic stem cell transplantation; PCR: polymerase chain reaction; PD: progressiv	ve disease; Peds: Pediatric; PET-CT: positron emission tomography-CT;
PF: pediatric short form; PGI-TT: Patient Global Impression of Treatment Tolerability; CC	PK: pharmacokinetic(s); PR: partial
response; PRO: patient-reported outcomes; PRO-CTCAE: Patient-Reported Outcomes version of the Co	ommon Terminology Criteria for Adverse Events; PTAP: post-trial Access
Program; Q6M: every 6 months; RECIL: Response Evaluation Criteria in Lymphoma; SAE: serious adv	erse event; SF: short form; SoA: Schedule of Activities; CC
CCI	

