#### Participants discontinuing study treatment while in response (PR/CR) or with SD:

Participants will enter the safety follow-up and will carry on with efficacy assessments by imaging until PD, start of a new anti-cHL therapy or EoS, whichever comes first (Table 4 and Table 16).

Note:

- Radiotherapy administered alone after the last dose of sabestomig while a participant is in CR, with a consolidation intent will not be considered as a new anti-cHL line of therapy. Therefore, the participant should carry on the efficacy follow-up and perform disease assessment by imaging as per SoA (Table 16).
- Participant in CR/PR who proceeds to HSCT without any treatment between the last dose of sabestomig and the start of the conditioning regimen will be followed-up for disease assessment post-transplant as per SoC and data on their disease status will be collected in the EDC as part of the survival follow-up.

See the SoA (Table 1, Table 2, Table 3, and Table 4) for data to be collected at the time of discontinuation of study intervention and follow-up and for any further evaluations that need to be completed.

If the participant does not agree to continue in-person study visits, a modified follow-up must be arranged to ensure the collection of endpoints and safety information. This could be a telephone contact with the participant, a contact with a relative or treating physician, or information from medical records. The approach taken should be recorded in the medical records. A participant who agrees to modified follow-up is not considered to have withdrawn consent or to have withdrawn from the study.

All participants in Safety or Survival follow-up at the time of final study DCO will be contacted by the study site prior to the final study DCO to confirm their survival status and to inform participants that this was the last study-related contact, and no further survival data will be collected in respect to the study. Sites are requested to document this last contact in the source records.

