## 8.1 Disease Response Assessment

Sites will be required to store electronic copies of all scans, and AstraZeneca will arrange for centralized storage of all imaging data. All imaging assessments, including unscheduled visit scans, will be collected on an ongoing basis and sent to AstraZeneca or designee for storage. The centralized storage of imaging data would allow independent centralized third-party blinded review of disease assessments. In this regard, and at the discretion of AstraZeneca, an independent central review of all scans used in disease assessment guidelines for imaging collection and storage will be provided in a separate document.

Participants will be evaluated by the Investigator for disease response using the Modified Lugano and RECIL criteria as secondary endpoints. Additionally, in Part B only, disease response will be evaluated by a BICR using Modified Lugano criteria. All participants will be followed up to evaluate OS. In the Part A of the study, imaging must be archived and transferred to the BICR to allow retrospective disease response assessment in participants treated at RP2D.

Efficacy assessments will be performed until PD/relapse, death, lost to follow-up, start of new treatment for cHL or withdrawal of the consent (whichever comes first). For participants discontinuing the study intervention due to other causes (eg, due to toxicities), disease follow-up will continue as per SoA until PD/relapse or start of new treatment for cHL is documented.

In the event pseudo progression is suspected by imaging, a PET-CT scan should be repeated at least 4 weeks after the previous assessment to confirm progression or response (Section 6.7) provided that the participants' clinical condition is stable. However, repeat imaging must be performed earlier than the next 12-week assessment where there is clinical suspicion of progression. The assessment of "clinically stable" must meet the following criteria:

- Absence of signs and symptoms (including worsening of laboratory values) indicating disease progression.
- No decline in ECOG performance status.
- Absence of rapid progression of disease.
- Absence of progressive tumor at critical anatomical sites (eg, cord compression) requiring urgent alternative medical attention.

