Radiological response should be integrated with clinical data and pathological findings, where available. Regardless of the radiological response, new or worsening of clinical findings indicative of lymphoma progression will result in an overall response of PD.

Unless unequivocally attributed to the disease, whenever possible the presence of a new lesion should be confirmed by biopsy. Biopsies at PD/relapse are not mandatory but recommended. If clinically indicated, unscheduled assessments can be performed at any time during the study.

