#### Radiological Assessments

Imaging is required for all participants, PET, and contrast CT scans to be performed as indicated in the SoA and in Table 16. If the study treatment is discontinued prior to PD, participant in response PR or CR (including participant in CR who received radiotherapy with consolidation intent) or stable disease will continue to be monitored for efficacy until PD, death, start of a new anti-cHL treatment, whichever comes first as per Table 16. If the treatment is discontinued prior to Year 1, the timepoints for disease assessment should follow approximately those of regular treatment administration.

**Note:** participant in CR/PR who proceeds to HSCT without any treatment between the last dose of sabestomig and the start of the conditioning regimen will be followed-up for disease assessment post-transplant as per SoC and data on their disease status will be collected in the EDC as part of the survival follow-up.

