4.2.6.2 Derivations

PFS (months) = (date of PFS event [progression/death] or censoring – date of first dose + 1) / (365.25/12).

Participants who have not progressed or died at the time of analysis, or have unknown status, are censored at the time of the latest date of assessment from their last evaluable disease assessment. However, if the participant progresses or dies immediately after two or more consecutive missed visits, the participant is censored at the time of the latest evaluable disease assessment prior to the two missed visits. Note: a NE visit is not considered as a missed visit.

If the participant has no evaluable disease assessments post-baseline or does not have baseline tumor assessment data they are censored at Day 1, unless they die within 57 weeks (i.e, 2 missed visit after Year 1 whereby disease assessments are every 6 months [2 x 26 weeks + 5 week for late visit = 57 weeks]) then the death qualifies as a PFS event. Participants who are censored at Day 1 are included in the FAS and the analysis but they do not contribute to any risk set. For participants who met one or more censoring conditions, PFS will be censored according to the earliest censoring condition; for participants who met none of the censoring conditions, PFS will be calculated by the earliest PFS event date.

A summary of censoring rules and the date of PD/death or censoring are given in Table 4.

Note that censoring overrides event in certain specified cases.

Table 4 Summary of Censoring Rules for PFS

Situation	Date of PD/Death or Censoring	PFS Outcome
Documented Progressive Disease (PD) or death in the absence of progression	Date of earliest documentation of PD or date of death	Event
Either no assessment at baseline or no evaluable assessments post-baseline AND death prior to Year 1 scheduled post-baseline disease assessment	Date of death	Event
Either no assessment at baseline or no evaluable assessments post-baseline AND no death prior to Year 1 scheduled post-baseline disease assessment	Date of first dose (Day 1)	Censored
PD or death (in the absence of progression) 57 weeks since previous disease assessments	Last evaluable progression-free disease assessment prior to missed assessments	Censored
At least one post-baseline tumor assessment, On- going with neither PD nor death at the time of analysis or lost to follow-up or withdrawn consent	Date of last evaluable disease assessment	Censored

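### Protocol Table 4 limits imaging after the Day 90 visit to participants still in response, while Sections 7.1 and 8.1.2 also continue it for stable disease, which risks informative censoring of PFS

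*Protocol*

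**What the plan says.** The passages on imaging after treatment stops are these.

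- **Protocol Table 4, imaging row.** Imaging goes on beyond the Day 90 post-last-dose visit "if participant still in response, until PD, start of new treatment for cHL or EoS (whichever occurs first". SD is not mentioned. The row and its footnote refer to Table 16 for the schedule.
- **Protocol Section 7.1.** Under the sub-heading "Participants discontinuing study treatment while in response (PR/CR) or with SD", participants "will carry on with efficacy assessments by imaging until PD, start of a new anti-cHL therapy or EoS, whichever comes first". The sentence cites both Table 4 and Table 16.
- **Protocol Section 8.1.2, Radiological Assessments.** Participants who stop before PD, in response "or stable disease will continue to be monitored for efficacy until PD, death, start of a new anti-cHL treatment", following Table 16.
- **Protocol Table 16.** After the Year 1 scan, imaging is every 6 months until end of study (EoS), with no condition on response.
- **Protocol Section 8.1.** For those who stop for other causes, with toxicity as the example, "disease follow-up will continue as per SoA until PD/relapse or start of new treatment for cHL is documented". It adds: "If clinically indicated, unscheduled assessments can be performed at any time during the study".

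On the analysis side, SAP Section 4.2.6.2 says that participants without a PFS event "are censored at the time of the latest date of assessment from their last evaluable disease assessment". It also says that "if the participant progresses or dies immediately after two or more consecutive missed visits, the participant is censored" at the last evaluable assessment before the gap. The SAP's own censoring table expresses that gap as 57 weeks.

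**The concern.** A participant who stops drug for toxicity with SD keeps having scheduled scans under Sections 7.1 and 8.1.2 and Table 16. Read literally, the Table 4 row gives no scheduled scan after about Day 90. Sites have some reason to work from Table 4: Section 8 makes adherence to the Schedule of Activities essential, and Section 8.1 sends participants who stop for toxicity back to that schedule. Practice could therefore differ between sites.

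PFS, with 12- and 24-month landmarks, is a secondary endpoint in both parts and is derived from scan or assessment dates. In Part B it is read by blinded independent central review from the transmitted images, so ending scheduled scans removes most of the means of dating progression. The supportive Part B analysis in SAP Section 4.2.6.4 changes the assessor to the Investigator but would lack the same scans. If participants with SD off drug progress faster than those who stay under imaging, censoring them early is informative and pushes the Kaplan-Meier estimate up. Later analysis could not recover the missing scans.

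**Working it through.** **1. Text comparison**

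| Passage | Participant off drug in CR/PR | Participant off drug with SD |
|---|---|---|
| Table 4 row | imaging past Day 90 | not provided for |
| Section 7.1 | to PD, new therapy or EoS | to PD, new therapy or EoS |
| Section 8.1.2 | to PD, death or new treatment | to PD, death or new treatment |
| Table 16 | every 6 months to EoS | every 6 months to EoS |
| Section 8.1 | as the schedule says | as the schedule says |

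The conflict is confined to the response condition in one row.

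**2. What the SAP would do.** With no further scan and no death, PFS is censored at the last evaluable scan. A death counts as an event unless it follows the gap. The SAP's gap reproduces: 2 x 26 + 5 = 57 weeks. A participant who starts new anticancer therapy before PD is censored at the last prior scan under every reading (bone marrow transplantation in response is treated separately), so the passages make no difference there.

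**3. Size.** The documents give no PFS rate, no share with SD and no rate of stopping drug in SD, and the on-treatment scan cycles are blacked out. There is no plan figure to reproduce. Both calculations below rest on assumed inputs.

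*Near-worst case.* Two exponential groups: B (share s, SD off drug) has median PFS 3 months, and A (the rest) has 12 months. All of B still under follow-up are censored at month c. Deaths after the last scan and unscheduled scans are ignored.

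True PFS(12) = (1-s)A(12) + sB(12)

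KM(12) = [(1-s)A(c) + sB(c)] x A(12)/A(c)

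A(3) = 0.841, A(6) = 0.707, A(12) = 0.5; B(3) = 0.5, B(6) = 0.25, B(12) = 0.0625.

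- s = 0.1: true = 0.9 x 0.5 + 0.1 x 0.0625 = 45.6%. KM = 48.0% (c = 3) or 46.8% (c = 6).
- s = 0.2: true = 0.8 x 0.5 + 0.2 x 0.0625 = 41.3%. KM = 46.0% (c = 3) or 43.5% (c = 6).

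The overstatement is about 1 to 5 points.

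*Illustrative simulation.* 20,000 participants per scenario, comparing imaging of SD to PD with imaging of SD ended 90 days after the last dose. Assumed scans are at weeks 9, 18, 36, 52, 78 and 104. SD progression time is 10 weeks plus an exponential time with the median shown. Participants with neither response nor SD progress at week 4. Deaths within 57 weeks of the last scan count as events. Median survival after progression is 104 weeks (52 in the row marked *). The affected share is the proportion of all participants who stop drug with SD before PD.

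| Responders / SD | Median weeks, responders / SD | Affected share | 12-month PFS, to PD vs Table 4 | 24-month PFS, to PD vs Table 4 |
|---|---|---|---|---|
| 60% / 20% | 78 / 26 | 1.3% | 44.0 vs 44.4 | 25.4 vs 25.7 |
| 60% / 20% | 78 / 26 | 4.1% | 44.2 vs 45.0 | 25.5 vs 26.3 |
| 60% / 20% | 78 / 26 | 6.6% | 44.0 vs 45.3 | 25.2 vs 26.6 |
| 40% / 35% | 52 / 26 | 7.4% | 31.2 vs 32.0 | 12.7 vs 13.4 |
| 40% / 35% | 52 / 26 | 11.9% | 31.7 vs 32.9 | 13.0 vs 14.0 |
| 40% / 35% * | 52 / 26 | 12.3% | 31.5 vs 32.9 | 13.0 vs 13.7 |
| 60% / 30% | 52 / 52 | 12.0% | 46.8 vs 46.7 | 23.6 vs 23.0 |

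Where SD progresses faster, the Table 4 rule raises 12-month PFS by 0.4 to 1.4 points and 24-month PFS by 0.3 to 1.4 points. Where it does not (last row), the effect is nil or slightly reversed. Median PFS was the same under both rules in every scenario (52 or 36 weeks). Those medians fall on scan weeks, so a small shift would not show.

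**The case against.** The strongest reply is that the protocol, read whole, already gives the answer. The Table 4 row and its footnote point to Table 16, which has no response condition. Section 7.1 cites Tables 4 and 16 together for a rule that names SD, so the authors evidently meant one rule. Table 4 does not say that imaging stops for SD; it is silent. A site that follows the full protocol would do the scans.

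This narrows the point but does not dispose of it. A pointer to Table 16 does not cancel an added condition in the row that points to it, and Section 8.1 leads the toxicity case back to the schedule.

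A reader might infer that participants with SD are lost before progression. The documents do not support that. Imaging runs to about Day 90, survival follow-up continues, deaths inside the 57-week rule are PFS events, and unscheduled scans are allowed when clinically indicated.

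The objection to the 5-point figure also stands in part. It assumes that every affected participant is handled under Table 4, and its 3- and 12-month medians have no source in the documents. The modelled group also does not match its label: with a 3-month median from first dose, half have progressed by month 3 and three quarters by month 6. It marks an upper end and is not an expected value.

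**Conclusion.** The inconsistency is established from the text. The effect on PFS is a conditional risk. It needs sites to follow the Table 4 row over Sections 7.1 and 8.1.2, participants who stop drug with SD and start no new therapy, and faster progression in them than in those still imaged. If all three hold, Kaplan-Meier PFS is biased upward. The stronger reading, that PFS will be overstated, is not supported: none of the three conditions is shown in the documents, and with similar progression rates the bias vanishes.

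The size cannot be derived from the documents. A fair statement is about 0 to 1.4 points at 12 months under the illustrative assumptions, and up to about 5 points under near-worst-case ones.

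The consequence is limited. Protocol Section 9.1 plans no hypothesis test. The primary efficacy endpoints are ORR and CRR, and the No-Go and futility rules in Section 9.5 use those. They would be touched only if a participant with SD responded after imaging had ended, and that would lower the rate. The passages should still be reconciled, because they differ on how endpoint data are collected.

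**What to change.** Reconcile the imaging row of protocol Table 4 with Sections 7.1 and 8.1.2 and Table 16. Replace the condition on being in response with one on not having progressed (CR, PR or SD), so that assessment beyond the Day 90 post-last-dose visit continues until PD, start of new cHL treatment or EoS. The cost is one phrase in one table row and a note to sites. It adds no scan that Sections 7.1 and 8.1.2 do not already require, and the SAP censoring rules need no change.
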